7.0 TREATMENT PLAN/INTERVENTION

Protocol treatment is to begin \leq 14 days of registration. For questions regarding treatment, please see the study contacts page.

This phase II randomized study is comparing sorafenib alone (standard treatment at 400 mg orally twice a day) to the combination of sorafenib (400 mg orally twice a day) and everolimus (5mg orally once a day) in patients with RAI-refractory Hürthle cell thyroid cancer. This would be a 1:1 randomization.

In patients who are randomized to sorafenib alone, we would allow for a crossover to everolimus alone (10 mg orally daily) at time of progression as an exploratory cohort. If a patient does crossover to everolimus alone, everolimus must begin within 6 weeks of the last dose of sorafenib on study. If restaging imaging has not been done within 28 days before treatment with everolimus alone, it must be repeated.

At the time of crossover, pregnancy test must be repeated. Also, if it has been more than 3 months since the last lipid profile, the lipid profile must be repeated at crossover. Other lab tests and observations will be performed per study calendar in [Section 5.0](#).

Patients will remain on treatment as long as there is no progression of disease, excessive toxicity requiring the patient to come off of treatment, or the patient withdraws from treatment.

Arm 1:

Agent	Dose and Route	Frequency	Cycle Length (ReRx)
Sorafenib*	400 mg PO	Twice daily	28 days***

Arm 2:

Agent	Dose and Route	Frequency	Cycle Length (ReRx)
Sorafenib*	400 mg PO	Twice daily	28 days***
Everolimus**	5 mg PO	Once daily	28 days***

Crossover for Arm 1:

Agent	Dose and Route	Frequency	Cycle Length (ReRx)
Everolimus**	10 mg PO	Once daily	28 days***

* Sorafenib should be taken twice daily on an empty stomach one hour before or two hours after eating. This tablet should be swallowed whole and cannot be crushed or chewed.

** Everolimus should be administered once daily at approximately the same time each day with or without food. Tablets should be swallowed whole with a glass of water. The tablets must not be chewed or crushed and grapefruit juice or grapefruit should be avoided.

***After year 1, at the start of cycle 13, the cycle length will be 56 days.

7.1 CYP3A4 Inhibitors

Chronic concomitant treatment with strong inhibitors of CYP3A4 is not allowed during on this trial. The following drugs are EXAMPLES of strong inhibitors of CYP3A4 and are not allowed during treatment with sorafenib.

- Indinavir
- Clarithromycin
- Ketoconazole

Because lists of these agents are constantly changing, please consult and review any drugs for their potential to inhibit CYP3A4. Examples of resources that may be utilized include the product information for the individual concomitant drug in question, medical reference texts such as the Physicians' Desk Reference, the FDA and/or IUPUI websites, or your local institution's pharmacist.

7.2 CYP3A4 Inducers

Chronic concomitant treatment with strong inducers of CYP3A4 is not allowed during on this trial. The following drugs are EXAMPLES of strong inducers of CYP3A4 and are not allowed during treatment with sorafenib.

- Rifampin
- Carbamazepine

Because lists of these agents are constantly changing, please consult and review any drugs for their potential to induce CYP3A4. Examples of resources that may be utilized include the product information for the individual concomitant drug in question, medical reference texts such as the Physicians' Desk Reference, the FDA and/or IUPUI websites, or your local institution's pharmacist.

8.0 DOSE AND TREATMENT MODIFICATIONS

8.1 Ancillary therapy, concomitant medications, and supportive care

- 8.1.1 Patients should not receive any other agent which would be considered treatment for the primary neoplasm or impact the primary endpoint with the exception of thyroid hormone replacement in order to suppress the TSH.**
- 8.1.2 Patients should receive full supportive care** while on this study. This includes blood product support, antibiotic treatment, and treatment of other newly diagnosed or concurrent medical conditions. All blood products and concomitant medications such as antidiarrheals, analgesics, and/or antiemetics received from the first day of study treatment administration until 30 days after the final dose will be recorded in the medical records.
- 8.1.3 Treatment with hormones** or other chemotherapeutic agents may not be administered except for steroids given for adrenal failure; hormones administered for non-disease-related conditions (e.g., insulin for diabetes); and intermittent use of dexamethasone as an antiemetic in solid tumor protocols.
- 8.1.4 Antiemetics** may be used at the discretion of the attending physician.
- 8.1.5 Diarrhea:** This could be managed conservatively with loperamide. The recommended dose of loperamide is 4 mg at first onset, followed by 2 mg every 2-4 hours until diarrhea free (maximum 16 mg/day). The following supportive measures are also allowed: hydration, octreotide, and other antidiarrheals.
- 8.1.6 Palliative radiation therapy** may not be administered during active treatment. Patients who require radiation therapy during active treatment will be removed from protocol therapy due to disease progression. However, if the patient is randomized to the sorafenib alone arm, they may receive palliative radiation therapy for a symptomatic lesion prior to the crossover for everolimus if the following conditions are met: (1) there are RECIST 1.1 lesions present outside of the radiation field; (2) Everolimus is started 2 or more weeks after radiation therapy is completed; (3) Everolimus is started within 6 weeks of the last dose of sorafenib.
- 8.1.7 Alliance Policy Concerning the Use of Growth Factors**

Blood products and growth factors should be utilized as clinically warranted and following institutional policies and recommendations. The use of growth factors should follow published guidelines of the American Society of Clinical Oncology 2006 Update of Recommendations for the Use of White Blood Cell Growth Factors: An Evidence-Based, Clinical Practice Guideline. J Clin Oncol 24(19): 3187-3205, 2006.

Epoetin (EPO): Use of epoetin in this protocol is permitted at the discretion of the treating physician.

Filgrastim (G-CSF) and sargramostim (GM-CSF)

1. Filgrastim (G-CSF)/pegfilgrastim and sargramostim (GM-CSF) treatment for patients is discouraged.
2. Filgrastim/pegfilgrastim and sargramostim may be used:
 - a. For the treatment of febrile neutropenia the use of CSFs should not be routinely instituted as an adjunct to appropriate antibiotic therapy. However, the use of CSFs may be indicated in patients who have prognostic factors that are predictive of clinical deterioration such as pneumonia, hypotension, multi-organ dysfunction (sepsis syndrome) or fungal infection, as per the ASCO guidelines. Investigators should therefore use their own discretion in using the CSFs in this setting. The use of CSF (filgrastim/pegfilgrastim or sargramostim) must be documented and reported. (e.g. on CRFs per protocol requirements)
 - b. If filgrastim/pegfilgrastim or sargramostim are used, they must be obtained from commercial sources.

8.1.8 Palmer-plantar erythrodysesthesia (PPE) syndrome

PPE is a common side effect of **sorafenib**. Patients should use moisturizers, avoid heat exposure (direct sun, saunas, etc), treat calluses, and should report rash or symptoms. In order to proactively alleviate PPE, consider using prophylaxis before starting treatment. Examples of prophylaxis include: Moisturizers such as eucerin, urea cream.

8.1.9 Pneumonitis

Refer to the following table for SUGGESTED medical management of the pneumonitis associated with **everolimus**. These are not required and included to provide site guidance for management:

Grade of Pneumonitis	Investigations to utilize	Management of Pneumonitis
Grade 1	CT scans with lung windows and pulmonary function testing including: spirometry, DLCO, and room air O ₂ saturation at rest. Repeat chest x-ray/CT scan every 2 Cycles until return to baseline.	No specific therapy is required
Grade 2	CT scan with lung windows and pulmonary function testing including: spirometry, DLCO, and room air O ₂ saturation at rest. Repeat each subsequent Cycle until return to baseline. Consider bronchoscopy *	Symptomatic only. Prescribe corticosteroids if cough is troublesome.
Grade 3	CT scan with lung windows and pulmonary function testing including: spirometry, DLCO, and room air O ₂ saturation at rest.; Repeat each subsequent Cycle until return to baseline. Bronchoscopy is recommended *	Prescribe corticosteroids if infective origin is ruled out. Taper as medically indicated.
Grade 4	CT scan with lung windows and required pulmonary function testing includes: spirometry, DLCO, and room air O ₂ saturation at rest. Repeat each subsequent Cycle until return to baseline. Bronchoscopy is recommended *.	Prescribe corticosteroids if infective origin is ruled out. Taper as medically indicated.

*A bronchoscopy with biopsy and/or bronchoalveolar lavage is recommended.

8.1.10 Stomatitis

The following are recommendations for stomatitis management associated with **everolimus**, to provide sites with guidance and are not required:

- For mild toxicity (Grade 1), use conservative measures such as **non-alcoholic mouth wash or salt water (0.9%) mouthwash** several times a day until resolution.
- For more severe toxicity (Grade 2 or 3), the suggested treatments are **topical analgesic mouth treatments**, with or without **topical corticosteroids**
- Antifungal and antiviral agents should be avoided due to drug interaction concerns

8.1.11 Hyperglycemia

Patients taking **everolimus** should be treated with appropriate medical therapy for hyperglycemia.

8.1.12 Hyperlipidemia

Patients taking **everolimus** should be treated with appropriate medical therapy for hyperlipidemia and avoiding concomitant medications that interact with study medication.

8.2 Dose Modifications for Sorafenib

- If multiple adverse events are seen, administer dose based on greatest reduction required for any single adverse event observed. Reductions or increases apply to treatment given in the preceding cycle and are based on adverse events observed since the prior dose.
- Sorafenib will not be re-escalated once reduced
- If dose reductions beyond dose level -2 is required or sorafenib is held for 4 weeks, sorafenib will be discontinued.
- If more than one of these toxicities apply, use the most stringent criteria (i.e., the greatest dose reduction.)
- If the patient experiences a significant adverse event requiring a dose reduction at the start of the next cycle, then the dose will remain lowered.

CTEP-AERS reporting may be required for some adverse events (See [Section 9.0](#))

8.2.1 Dose levels

Dose reduction of sorafenib will be performed according to the table below. Sorafenib will be permanently discontinued for patients who require dose interruptions of > 28 days or who experience dose limiting toxicities at dose level -2. Missed doses of sorafenib will not be made up.

Dose Level	Drug Name	Dose
0*	Sorafenib	400mg twice daily
-1	Sorafenib	200mg twice daily
-2	Sorafenib	200mg daily

*Dose level 0 refers to the starting dose.

- If dose reductions beyond the lowest dose level are required discontinue all protocol therapy.
- Doses that have been reduced will not be re-escalated.

8.2.2 Dose Modifications for Hematologic Toxicities

Grade ≥ 3 neutropenia, thrombocytopenia, or neutropenic fever: Interrupt sorafenib until \leq grade 2, then resume with one dose level reduction of sorafenib for all subsequent doses.

8.2.3 Dose Modifications for Gastrointestinal Toxicities

- **Grade 2 diarrhea:** Interrupt sorafenib until diarrhea improves to \leq grade 1, then resume sorafenib at same dose level.
- **Grade ≥ 3 diarrhea:** Interrupt sorafenib until diarrhea improves to \leq grade 2, then resume sorafenib with one dose level reduction.
- **GI Perforation:** Discontinue sorafenib.

8.2.4 Dose Modifications for Hepatic Dysfunction

- **Grade 2 blood bilirubin increased:** Interrupt sorafenib until improved to grade 1, then resume sorafenib at same dose.
- **Grade 3 blood bilirubin increased:** Interrupt sorafenib until improved to grade 1, then resume sorafenib at 1 dose level reduced.
- **Grade 4 blood bilirubin increased:** Discontinue sorafenib.
- **Grade 3 transaminase increased:** Interrupt sorafenib until improved to grade 1, then resume sorafenib at 1 dose level reduced.
- **Grade 4 transaminase increased:** Discontinue sorafenib.

8.2.5 Dose Modifications for Hypertension

- **For hypertension $>140/90$ and $\leq 160/100$:** Continue sorafenib. Consider adding or adjusting anti-hypertensive medications (e.g., calcium channel blockers as per institution's guideline for HTN treatment).
- **For persistent ($>160/100$) or symptomatic hypertension:** Interrupt sorafenib. Resume when blood pressure improves to $\leq 160/100$. If sorafenib is interrupted for > 4 weeks, discontinue sorafenib therapy.
- **Grade 4 hypertension:** Discontinue all sorafenib therapy.

8.2.6 Dose Modifications for Cardiotoxicity

- **Myocardial ischemia:** Discontinue sorafenib.

8.2.7 Dose Modifications for Skin Toxicity (palmar-plantar erythrodysesthesia (PPE) syndrome)

Skin Toxicity	Occurrence	Suggested Dose Modification
Numbness, dysesthesia, paresthesia, tingling, painless swelling, erythema or discomfort of the hands or feet relief which does not disrupt the patient's normal activities	Any occurrence	Continue treatment with sorafenib and consider topical therapy for symptomatic relief
Painful erythema and swelling of the hands or feet and/or discomfort affecting the patient's normal activities	1st occurrence	Continue treatment with sorafenib and consider topical therapy for symptomatic relief. If no improvement within 7 days, see below
	No improvement within 7 days or 2nd or 3rd occurrence	Interrupt sorafenib until toxicity resolves to Grade 0-1. When resuming treatment, decrease sorafenib dose by one dose level

	4th occurrence	Discontinue sorafenib
Moist desquamation, ulceration, blistering or severe pain the hands or feet, or severe discomfort that causes the patient to be unable to work or perform activities of daily living	1st or 2nd occurrence	Interrupt sorafenib until toxicity of resolves to Grade 0-1. When resuming treatment, decrease sorafenib dose by one dose level
	3rd occurrence	Discontinue sorafenib

8.2.8 Dose Modifications for Other Non-hematologic Toxicities

For other clinically significant grade 3/4 non-hematologic toxicities likely related to sorafenib, interrupt sorafenib. Resume sorafenib at 1 dose level reduced when the toxicity resolves to a clinically acceptable level (grade 1/2).

8.3 Dose Modifications for Sorafenib + Everolimus

- If multiple adverse events are seen, administer dose based on greatest reduction required for any single adverse event observed. Reductions or increases apply to treatment given in the preceding cycle and are based on adverse events observed since the prior dose.
- Sorafenib or everolimus will not be re-escalated once reduced
- If dose reductions beyond dose lowest dose level is required OR sorafenib or everolimus is held for 4 weeks, sorafenib or everolimus will be discontinued. If 1 agent is discontinued, the patient may remain on the other agent. If sorafenib is discontinued and everolimus has never been dose reduced, the patient may have everolimus dose increased to 10 mg daily. In this scenario, dose level chart for everolimus in [section 8.4.1](#) should be used.
- If more than one of these toxicities apply, use the most stringent criteria (i.e., the greatest dose reduction.).

CTEP-AERS reporting may be required for some adverse events (See [Section 9.0](#))

8.3.1 Dose levels

Dose reduction of sorafenib and everolimus will be performed according to the table below. Sorafenib or everolimus will be permanently discontinued for patients who require dose interruptions of > 28 days or who experience dose limiting toxicities at dose level -2. Missed doses of sorafenib or everolimus will not be made up. To clarify, only the dose level of the offending agent needs to be dose reduced as per protocol if it is clear that the other drug did not cause the adverse event (e.g., only sorafenib needs to be dose reduced for hand-foot syndrome). If there are any questions, please discuss with protocol PI ([name]).

Dose Level	Drug Name	Dose	Drug Name	Dose
0*	Sorafenib	400 mg twice daily	Everolimus	5mg daily
-1	Sorafenib	200 mg twice daily	Everolimus	2.5mg daily
-2	Sorafenib	200mg daily	Everolimus	2.5mg every other day

*Dose level 0 refers to the starting dose.

8.3.2 Dose Modifications for Hematologic Toxicities

- **Grade 2 thrombocytopenia:** Interrupt sorafenib and everolimus until grade ≤ 1 , then resume sorafenib and everolimus at same dose.

- **Grade ≥ 3 neutropenia, grade ≥ 3 thrombocytopenia, or neutropenic fever:** Interrupt sorafenib and everolimus until \leq grade 2, then resume with one dose level reduction of sorafenib and everolimus for all subsequent doses.

8.3.3 Dose Modifications for Gastrointestinal Toxicities

- **Grade 2 diarrhea:** Interrupt sorafenib and everolimus until diarrhea improves to grade ≤ 1 then resume at same dose.
- **Grade ≥ 3 diarrhea:** Interrupt sorafenib and everolimus until diarrhea improves to \leq grade 2, then resume sorafenib and everolimus with one dose level reduction of both agents.
- **GI Perforation:** Discontinue sorafenib.
- **Grade 3 stomatitis:** Interrupt everolimus until \leq grade 1 then resume with one dose level reduced.
- **Grade 4 stomatitis:** Discontinue everolimus.

8.3.4 Dose Modifications for Hepatic Dysfunction

- **Grade 2 blood bilirubin increased:** Interrupt sorafenib and everolimus until improved to grade 1, then resume sorafenib and everolimus at same dose.
- **Grade 3 blood bilirubin increased:** Interrupt sorafenib and everolimus until improved to grade 1, then resume sorafenib and everolimus at 1 dose level reduced.
- **Grade 4 blood bilirubin increased:** Discontinue sorafenib and everolimus.
- **Grade 3 transaminase increased:** Interrupt sorafenib and everolimus until improved to grade 1, then resume sorafenib and everolimus at 1 dose level reduced.
- **Grade 4 transaminase increased:** Discontinue sorafenib and everolimus.

8.3.5 Dose Modifications for Hypertension

- **For hypertension $>140/90$ and $\leq 160/100$:** Continue sorafenib. Consider adding or adjusting anti-hypertensive medications (e.g., calcium channel blockers as per institution's guideline for HTN treatment)).
- **For persistent ($>160/100$) or symptomatic hypertension:** Interrupt sorafenib. Resume when blood pressure improves to $\leq 160/100$. If sorafenib is interrupted for > 4 weeks, discontinue sorafenib therapy.
- **Grade 4 hypertension:** Discontinue sorafenib

8.3.6 Dose Modifications for Cardiotoxicity

Myocardial ischemia: Discontinue sorafenib.

8.3.7 Dose Modifications for Skin Toxicity

- **Palmar-plantar erythrodysesthesia (PPE) syndrome**

Skin Toxicity	Occurrence	Suggested Dose Modification
Numbness, dysesthesia, paresthesia, tingling, painless swelling, erythema or discomfort of the hands or feet relief which does not disrupt the patient's normal activities	Any occurrence	Continue treatment with sorafenib and consider topical therapy for symptomatic relief
Painful erythema and swelling of the hands or feet and/or discomfort affecting the patient's normal	1st occurrence	Continue treatment with sorafenib and consider topical therapy for symptomatic relief. If no improvement within 7 days,

activities	see below	
	No improvement within 7 days or 2nd or 3rd occurrence	Interrupt sorafenib until toxicity resolves to Grade 0-1. When resuming treatment, decrease sorafenib and everolimus dose by one dose level
	4th occurrence	Discontinue sorafenib
Moist desquamation, ulceration, blistering or severe pain the hands or feet, or severe discomfort that causes the patient to be unable to work or perform activities of daily living	1st or 2nd occurrence	Interrupt sorafenib until toxicity of resolves to Grade 0-1. When resuming treatment, decrease sorafenib dose by one dose level
	3rd occurrence	Discontinue sorafenib

- **Grade 4 Acneiform Rash:** Interrupt everolimus until grade ≤ 2 , then restart at one dose level decreased
- **Grade 3 Maculopapular Rash:** Interrupt sorafenib and everolimus until grade ≤ 2 , then restart sorafenib and everolimus at one dose level decreased

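### In the combination arm, one row of the section 8.3.7 hand-foot syndrome table also reduces everolimus, although section 8.3.1 gives hand-foot syndrome as its example of reducing sorafenib only

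*Combined protocol and SAP*

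**What the plan says.** Two parts of protocol section 8.3, which governs dose changes for sorafenib plus everolimus, address hand-foot syndrome (palmar-plantar erythrodysesthesia, PPE).

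- **Section 8.3.1 (dose levels).** It states a general rule: "To clarify, only the dose level of the offending agent needs to be dose reduced as per protocol if it is clear" (the condition being that its partner was not responsible). The example it gives is that "only sorafenib needs to be dose reduced for hand-foot syndrome". Questions go to the protocol PI.
- **Section 8.3.7 (PPE table).** In the middle severity category, when the event has not improved after 7 days or is a second or third occurrence, sorafenib is interrupted until Grade 0-1. The row then says: "When resuming treatment, decrease sorafenib and everolimus dose by one dose level". The column is headed "Suggested Dose Modification".

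The more severe category of the same table, first or second occurrence, says: "Interrupt sorafenib until toxicity of resolves to Grade 0-1. When resuming treatment, decrease sorafenib dose by one dose level". The sorafenib-alone table in section 8.2.7 words the middle row as: "Interrupt sorafenib until toxicity resolves to Grade 0-1. When resuming treatment, decrease sorafenib dose by one dose level".

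The general rules of section 8.3 add that "Sorafenib or everolimus will not be re-escalated once reduced" and that "If 1 agent is discontinued, the patient may remain on the other agent". If sorafenib is stopped and everolimus has never been reduced, everolimus may be raised to 10 mg daily.

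**The concern.** The two sections give different everolimus doses for the same toxicity in the same arm. A site that applies section 8.3.1 keeps everolimus at 5 mg daily. A site that looks up the toxicity in section 8.3.7 and does what the row says lowers it to 2.5 mg daily.

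This matters because everolimus is the only randomized difference between the arms. The lower dose is permanent, and a single reduction removes the later option of 10 mg daily. Section 13.2 keeps every eligible, consented, randomized patient in the primary PFS comparison whatever dose was received, so any unneeded everolimus reduction is carried into that comparison.

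**Working it through.** **1. The texts side by side**

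| Place | Drug interrupted | Drug reduced on resuming |
|---|---|---|
| 8.3.1, hand-foot example | not stated | sorafenib |
| 8.3.7, middle category, not better after 7 days or 2nd/3rd occurrence | sorafenib | sorafenib **and everolimus** |
| 8.3.7, severe category, 1st/2nd occurrence | sorafenib | sorafenib |
| 8.2.7, matching middle row (sorafenib alone) | sorafenib | sorafenib |

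Of the six occurrence rows in the 8.3.7 PPE table, only this one names everolimus. Two rows call for a reduction, and the milder of the two is the one that also lowers everolimus.

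**2. Comparison with the other named-toxicity rules in section 8.3 that interrupt and then reduce**

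- Both drugs interrupted and both reduced: grade 3 or higher hematologic toxicity, grade 3 or higher diarrhea, grade 3 bilirubin, grade 3 transaminases, grade 3 maculopapular rash.
- Everolimus interrupted and everolimus reduced: grade 3 stomatitis, grade 4 acneiform rash, grade 2 or 3 pneumonitis, grade 2 creatinine, grade 3 edema.
- Sorafenib interrupted and sorafenib reduced: severe PPE.

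The middle PPE row is the only rule that reduces a drug it does not interrupt.

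**3. Everolimus dose per 28 days** (dose levels from section 8.3.1)

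- Level 0: 5 mg × 28 = 140 mg
- Level -1: 2.5 mg × 28 = 70 mg, and (140 - 70)/140 = 50% lower
- Level -2: 2.5 mg every other day, 2.5 × 14 = 35 mg, and (140 - 35)/140 = 75% lower
- Optional increase after sorafenib is stopped: 10 mg × 28 = 280 mg

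**4. Repeated use of the row, starting at level 0**

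| Trigger | Sorafenib (either reading) | Everolimus, row followed | Everolimus, 8.3.1 followed |
|---|---|---|---|
| 1st | 200 mg twice daily | 70 mg | 140 mg |
| 2nd | 200 mg daily | 35 mg | 140 mg |
| 3rd | below level -2, discontinued | 35 mg, no further step | 140 mg, optionally 280 mg |

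At the third trigger sorafenib is not resumed, so the row causes no further everolimus step. At that outer limit the two readings differ by 140/35 = 4-fold, or 280/35 = 8-fold if the 10 mg option is used. After one use of the row and a later sorafenib stop, the gap with the option is 280/70 = 4-fold.

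**5. Frequency**

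Section 1.3 reports hand-foot syndrome in more than 20% of patients in the phase I kidney cancer study of this combination, with no grade given. If that rate applied here (an assumption), more than 0.20 × 15 = 3.0 of the evaluable patients in the combination arm would have it, or more than 0.20 × 17 = 3.4 at full accrual. The share who would reach this row is not given and could be anywhere from none to all of them.

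**The case against.** The strongest reply is that the protocol largely resolves the mismatch itself. The section 8.3.1 sentence is offered as a clarification, names this very toxicity, and stands directly before the dose-level table that a site needs in order to carry out the row. The 8.3.7 column only suggests. Section 8.3.1 is conditional, does not forbid lowering everolimus, and sends questions to the protocol PI. Section 10.2 lists PPE among everolimus toxicities at 1-10%, so the dual reduction may have been intended. The 4-fold and 8-fold figures need several events in sequence, none with a stated probability, and no effect on PFS is shown.

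Much of this stands. The passages are inconsistent guidance and not incompatible mandates, and a careful site may well settle on section 8.3.1. A slip is likely but not certain. The realistic unit of harm is one step, 5 mg to 2.5 mg daily; the larger ratios are an outer limit only.

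It does not remove the inconsistency. Section 8.3.1 chooses hand-foot syndrome as its sorafenib-only case, and the row instructs otherwise. Section 8.1.8 attributes PPE to sorafenib, and the everolimus risk list in section 9.4.2 places PPE among events with insufficient evidence of causation. The rule in section 8.3 to apply the most stringent criteria concerns several toxicities at once, so it does not settle two instructions for one toxicity. Nor would an intended dual reduction explain why the more severe row spares everolimus.

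**Conclusion.** The concern holds. One row of section 8.3.7 is inconsistent with section 8.3.1, with the more severe row of its own table, and with the interrupt-then-reduce pattern of the other named-toxicity rules in section 8.3. Following it once permanently halves everolimus and forfeits the optional 10 mg dose. From the starting dose it can act at most twice, leaving 35 mg per 28 days.

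The dose figures are arithmetic on the protocol's own levels. The patient count rests on assuming that the phase I rate carries over, and the share reaching the row is unknown. Sample size, power and the analysis plan are unaffected, and no effect on the trial result is shown. The point should still be corrected, because this is an operative dosing instruction for the one randomized drug, it cannot be reversed for the patient concerned, and it is cheap to put right.

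**What to change.** Delete the words naming everolimus from the middle-category reduction row of the 8.3.7 PPE table, so that it matches section 8.3.1, the more severe row and section 8.2.7. Notify sites. Section 8.3.12 still allows an everolimus reduction for clinically significant grade 3/4 toxicity judged likely related to it. If the study chair confirms that the dual reduction was intended, change the example in section 8.3.1 instead and say why the more severe row differs.

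The cost is a two-word deletion in the next amendment and a site notice.
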